Appendix 12: Procedures for nucleic acid (NAT) testing for infection with HIV, HCV, and HBV

- CRUSH staff will collect blood at all visits from HIV-negative participants not receiving PrEP for HIV/HCV/HBV NAT testing.
- Each blood sample will be labeled using a unique, de-identified, five-digit number barcoded sticker provided by the Red Cross. Participants will also be given this 5-digit number so that they may retrieve their HIV test results (if negative) via the web or interactive voice response system two weeks after their test date.
- Samples will be sent in batches directly to the American Red Cross reference laboratory in St. Louis, MO for NAT testing three times a week, and CRUSH staff will notify the University of California, San Diego Antiviral Research Center (AVRC) staff via a secure web form that a NAT test was performed (only 5-digit code and test date entered).
- After the Red Cross completes NAT testing (usually within 5 days), the Red Cross will send the encrypted results electronically to the UCSD Center for AIDS Research (CFAR) Bioinformatics and Information Technologies (BIT) Core via secure FTP.
- Upon receiving the results from the Red Cross, the UCSD BIT Core will automatically decrypt the results and import them into a secure database located on servers hosted at the UCSD San Diego Supercomputing Center (SDSC) and Antiviral Research Center (AVRC).
- The decrypted results will be matched up to the 5-digit code provided by CRUSH staff to the AVRC via the above-mentioned web form. This matching allows the BIT Core to monitor the flow of data closely should any reporting fail between Oakland, the Red Cross and the AVRC.
- In cases of negative HIV NAT results, participants can obtain their results two weeks after testing via web or interactive voice response using their 5-digit code, at theearlytest.ucsd.edu
- For HIV positive results, AVRC staff and CRUSH staff will be automatically notified via email (including only 5-digit code, test date, and positive result) by BIT Core scripts. This allows

sufficient time for clinical staff to directly contact positive individuals before the two-week negative results access window opens.

- HCV and HBV negative results are not made available to participants through the web or interactive voice response, but positive results will be reported via email to AVRC and CRUSH staff so that they may directly contact participants.

UCSD Center for AIDS Research (CFAR) Bioinformatics and Information Technologies (BIT) Core security and privacy features:

The BIT Core has at its disposal 700+ processor Linux Beowulf MPI cluster, seven rack-mounted web servers, and two fault-tolerant encrypted 16TB RAID6 data storage arrays. All primary production machines are located behind a hardware firewall at the SDSC on the UCSD main campus in a server facility with biometric-based restricted access, temperature and humidity monitoring, seismic protection, 24/7 generator power backup, and continuous CCTV camera surveillance. For data and service redundancy in case of hardware or power failure at SDSC, secondary backup machines are located behind a hardware firewall at the UCSD Antiviral Research Center AVRC on the UCSD medical campus in a server room with key card-based restricted access, temperature and humidity monitoring, and 24/7 CCTV camera surveillance.

Appendix 13: Allele-specific PCR-based minor variant drug resistance assay

The development of drug-resistant virus in individuals who become infected while taking PrEP is a concern that warrants close monitoring. While the detection of FTC-TDF selected drug resistance in clinical trial participants who fail PrEP is rarely seen using conventional genotyping and ultrasensitive assays, continued study and monitoring is needed as FTC-TDF PrEP use is expanded to non-research settings. Ongoing and planned demonstration projects present an ideal opportunity to monitor the incidence and nature of drug resistance selected by PrEP.

HIV-1 drug resistance testing for the CRUSH PrEP demonstration project will be performed at UCSF's AIDS Research Institute Laboratory of Clinical Virology (ARI-UCSF LCV) using specimens collected from HIV infected participants at first evidence of infection. HIV-1 genotypic resistance testing will be performed by bulk sequencing of the protease and reverse transcriptase region using the FDA-cleared TRUGENE genotyping kit under clinical protocols. Individual drug resistance mutations and drug susceptibility interpretations are reported. For increased sensitivity, a validated allele-specific PCR-based minor variant drug resistance assay will be performed for detection of minor variant drug resistance at FTC/TDF-selection codons K65R, K70E, and M184V/I that may be present at a low level, and not detected by the sequence-based assay. The % drug resistance codon above the biologic cutoff (BCO) at each drug resistance site is reported.

A single specimen is used for both assays. Specimens of at least 1.0 mL blood plasma will be obtained from participants, spun, and frozen, then sent to [name] lab, with no identifying information except for a unique identifier code number. A minimum HIV-1 viral load of 500 copies/mL by standard commercial assays is required. Results will be reported back to CRUSH staff by code number.

## Statistical Analysis Plan

Descriptive statistics (frequencies, means, medians) will be used to characterize endpoint variables. Univariate tests of association (T test, Chi square) will be used to test for association between demographic variables and key endpoints such as adherence, early cessation of regimen, and frequency of adverse events, as well as between assigned PEP regimen and these endpoints. Changes in quality of life will be tested for association with early regimen cessation and with assigned PEP regimen. Changes in serum creatinine will be summarized with descriptive statistics (mean, standard deviation) and compared to historical data from clinical trials.

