Aim 1: Test and link young MSM of color to sexual health services: We will expand our currently successful HIV testing strategy—***collaborations and systems of referral of new cases of HIV from existing partners***—so that referrals are also received for high risk negatives to receive sexual health services. We will also implement two new strategies: an enhancement we have used successfully in prior

projects—*social network testing*; and an innovative strategy derived from evidence from our pilot study—a *youth outreach corps working with existing and new community partner agencies*.

Aim 2: Enhance and evaluate engagement and retention strategies for young MSM of color infected with HIV: We will plan to optimize the current HIV care and treatment services at DYC by adding three new components: a *patient peer mentoring component*; a *linkage and retention specialist*; and *psychosocial support for program staff*.

Aim 3: Engage and retain HIV-uninfected young MSM of color in sexual health services, including PrEP: Finally, at the heart of the CRUSH project is our plan to build a highly innovative and much needed model of sexual healthcare that integrates sexual health services for HIV-uninfected young MSM of color into an HIV care

setting. These services will replicate the developmentally appropriate, culturally sensitive aspects of the DYC model to offer a highly effective combination HIV prevention strategy, including PrEP, and also: *warm-hand offs for high risk*

Connecting Resources for Urban Sexual Health (CRUSH)

Aim 1: Testing and Linkage

- Downtown Youth Clinic (DYC)*
 - Existing model/services
 - Social network HIV testing and linkage*

- Partnerships with existing youth-serving clinics
 - Continuing referrals for new HIV-positives
 - New referrals for HIV-negatives*

- Community engagement with new partners
 - Youth corps, embedded outreach and testing coordinators*
 - Internet outreach*

CRUSH

- Intake
- Triage

HIV Positive

Aim 2: Enhanced HIV Primary Care for Youth

- DYC + Enhancements*
 - Assisted disclosure and warm hand off
 - Existing services*
 - Peer mentoring*
 - Linkage/Retention specialist*
 - Staff support*

HIV Negative

Aim 3: Sexual Health Services for High-Risk HIV Negative Youth

- Sexual Health Services for HIV Negatives:*
 - Warm handoff to prevention case manager
 - PrEP
 - nPEP
 - Prevention counseling
 - Repeat testing (HIV, STI) every 3-6 months
 - Youth focused and youth run workshops*

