*See Existing Services Section

negatives; non-occupational post-exposure prophylaxis (nPEP) when indicated; risk reduction counseling; frequent HIV and STI testing, including testing a highly sensitive method of detecting early HIV infection; and youth-focused programming.

III. Study Population

We propose to target young MSM of color in the East Bay for a comprehensive intervention, which builds on our experience and includes culturally-competent HIV testing, sexual health services including pre-exposure prophylaxis (PrEP), and an integrated linkage and retention program into sexual health services for both high-risk HIV-negative men and HIV-positive men. More specifically **we will focus on African American, Chicano/Latino, and Asian/Pacific Islander MSM** under 30 in the most highly affected cities of western Contra Costa County and northern Alameda County including Oakland, San Pablo, Berkeley, Richmond, and San Leandro.

III.1 Eligibility of HIV Positive Individuals

- HIV positive individuals between the ages of 18-29.

Seropositives outside the target CRUSH age range will be referred for clinical care as appropriate at DYC, EBAC, or elsewhere.

III.2 Eligibility of HIV Negative Individuals

Among those who are HIV negative, we specifically aim to recruit the following most highly impacted communities in the East Bay:

- Men between the ages of 18-29 who are ever sexually active with men;
- Transgender females (M2F) between the ages of 18-29 who are sexually active with men;
- Transgender males (F2M) between the ages of 18-29 who are sexually active with men; and

- Any HIV negative person aged 18-29, male or female, who has at least one known HIV positive (i.e. serodiscordant) sexual partner;

All HIV positives and negatives who meet the eligibility above and present at the clinic will be offered a voluntary opportunity to consent for participation. Participants must meet eligibility criteria and must be willing and able to provide informed consent, utilizing English or Spanish language.

IV Specific Research Activities

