Samples will be collected for sexually transmitted infections (STI), serum HIV antibody, HBsAg and HBsAb testing. All participants who are subsequently found to be both HBsAg and HBsAb negative will be offered the hepatitis B vaccination series. Participants found to be HBsAg positive may still receive Truvada® PrEP, but will in addition be monitored according to a specific protocol. [See Appendix Q] Those found to be hepatitis B antigen positive, but who choose not to enroll in PrEP, will be referred to either their primary care provider or another community-based clinic for treatment of hepatitis B infection.

All HIV-negative participants, regardless of hepatitis B status, who are interested in receiving PrEP will receive further counseling on PrEP and, in addition to the blood work mentioned above, will have an HIV NAT sent. They will also meet with a clinician for medical history, a targeted physical exam and an assessment of PrEP eligibility according to criteria in Section IV. Assessment of eligibility will also

include an evaluation for symptoms of acute retroviral syndrome, including sore throat, fevers, sweats, headaches, myalgias or arthralgias, which are not consistent with seasonal or chronic patterns. If symptoms of acute retroviral syndrome are present in the setting of a recent high risk exposure, PrEP will be deferred until the results of the HIV NAT are back. If there has been a high risk exposure in the past 72 hours to potentially infectious body fluids from a partner who is HIV infected and who has a detectable or unknown viral load (i.e., who do not have a most recent undetectable HIV RNA below the limit of quantitation within the previous 90 days), or who is at high risk for being HIV-infected, post-exposure prophylaxis (PEP) will be offered using a recommended 3 drug regimen for 28 days. Preferred PEP regimens will be selected according to recently published guidelines of the USPHS for occupational PEP, and of the New York State Task Force.

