If a PrEP candidate has an identifiable HIV-positive partner, we will attempt to obtain genotypic information about the partner's virus, in order to avoid offering Truvada® PrEP in a situation of likely exposure to a virus already resistant to both component drugs of Truvada®. We will ask the PrEP candidate to try to obtain a de-identified genotype of the seropositive partner. We will assist in providing a release of confidential medical information form for this purpose. In the event that the seropositive partner is a patient at DYC, we will ask the seropositive partner to sign a 'Release of Information' allowing the PrEP participant and the CRUSH team access to his genotype. If a CRUSH medical provider has confirmed documentation that the seropositive partner's virus is resistant to both drugs in Truvada®, or has reason to believe that this is likely the case, then the PrEP patient will be excluded from receiving Truvada® PrEP as part of CRUSH, and will be referred for expert medical consultation regarding other options. If we are unable to obtain a genotype or resistant records for the seropositive partner, and have no reason to believe that two-drug resistance is likely, we will offer Truvada® PrEP as usual.

VII.7 PrEP Initiation

The PrEP initiation visit will take place 1-2 weeks after screening, when all screening results are available. If the participant is eligible to receive PrEP, the clinician will review all lab results done at the screening visit, repeat a rapid oral HIV antibody test, and obtain a medical history along with a focused review of systems. All participants who are determined to be HBsAg negative and who do not have antibodies to hepatitis B will be offered the hepatitis B vaccination series. If high risk exposure, as described in section VI 1.1, or signs and/or symptoms suggestive of acute retroviral syndrome have occurred since the screening visit, PrEP will be withheld and the participant will be managed in accordance with the guidelines specified in the screening visit. Further STI testing will also be done if indicated. Women of reproductive potential will have a rapid urine pregnancy test. If no contraindications to receiving PrEP have been established, the risks and benefits of FTC/TDF (Truvada®) for PrEP will be reviewed, and all questions and concerns will be addressed. The participant will be instructed to take FTC/TDF daily, at the same time every day. The study coordinator or other DYC staff

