### Secondary Endpoints(s):

- To assess the renal safety of Stribild® or Genvoya® or unbranded elvitegravir/cobicistat/emtricitabine/tenofovir alafenamide PEP
- To document the side effect profiles of Stribild® or Genvoya® or unbranded elvitegravir/cobicistat/emtricitabine/tenofovir alafenamide given as PEP to HIV-1 seronegative adults
- To assess adherence to Stribild® or Genvoya® or unbranded elvitegravir/cobicistat/emtricitabine/tenofovir alafenamide PEP in a high risk population of HIV-1 seronegative adults
- Early cessation of regimen
- Frequency of adverse events
- Change from baseline in quality of life
- HIV-1 seroconversion
- Change from baseline in serum creatinine and eGFR
- Markers of proximal tubulopathy (glycosuria, proteinuria > 1+)
- Self-reported adherence
- Reasons for non-adherence

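### The SAP text tests an assigned PEP regimen and names PEP products that have no counterpart in the CRUSH protocol text, so the two must be matched before analysis

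*SAP*

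**What the plan says.** **SAP.** The Statistical Analysis Plan section uses t tests and chi-square tests to relate demographic variables to endpoints such as adherence, early stopping and adverse events, "as well as between assigned PEP regimen and these endpoints". It uses the same factor a second time: "Changes in quality of life will be tested for association with early regimen cessation and with assigned PEP regimen". Under Secondary Endpoints, three objectives are tied to named products. The first begins "To assess the renal safety of Stribild® or Genvoya" and goes on to an unbranded version of the second product. The other two cover side effects and adherence for the same products.

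**Protocol, PEP.** Section II lists, as one service within Aim 3, "non-occupational post-exposure prophylaxis (nPEP) when indicated". Section VII.6 says how the drugs are chosen: "Preferred PEP regimens will be selected according to recently published guidelines of the USPHS for occupational PEP", together with New York State guidance. It describes a three-drug course and names no drug.

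**Protocol, PrEP and aims.** For the start of PrEP, Section VII.7 says that "the risks and benefits of FTC/TDF (Truvada®) for PrEP will be reviewed". Sections VII.7 to VII.9 then set out Truvada dispensing and monitoring. In Section II, Aim 1 is testing and linkage, the next is stated as "Aim 2: Enhance and evaluate engagement and retention strategies for young MSM of color infected with HIV", and Aim 3 is engagement and retention of HIV-negative participants, with PrEP.

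**Protocol, NAT.** Section VII.3 tests every HIV-negative participant at each visit. Appendix 12 collects the sample only from HIV-negative participants who are not on PrEP.

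**The concern.** A comparison of regimens needs groups that are fixed before outcomes are known, and the protocol is where one looks for them. The SAP treats the PEP regimen as something assigned, yet the protocol text contains no such assignment and none of the products. Three things are at stake.

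- Without a definition, who counts as being on which PEP regimen could be decided once the data are in hand.
- If the rest of the SAP is like the part seen, the product that the protocol does study, and its three aims, would have no prespecified analysis.
- The yield of NAT, which Section VII.3 makes a study question in its own right, could be reported over two different denominators.

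**Working it through.** The documents give no sample size, error rate or effect size for the regimen comparison, so this check sets the texts side by side. The review had the SAP only from its Statistical Analysis Plan heading onward, and the protocol without the pages between Appendix 1 and Appendix 4.

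**1. What the SAP rests on PEP regimen or product.** Endpoints named for testing against regimen: adherence, early cessation and adverse events (3), plus change in quality of life (1), so 3 + 1 = 4. The secondary list has 11 items; 3 name the products and 11 − 3 = 8 do not.

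**2. Counterparts in the protocol text.**
- Products: Stribild, Genvoya, elvitegravir, cobicistat and tenofovir alafenamide have 0 mentions.
- Assignment: no passage allocates participants to PEP regimens or compares regimens.
- Follow-up: the columns of the Appendix 4 schedule are screening, week 0, week 4, weeks 12 to 48, stopping drug, and a positive HIV antibody test. None is for a PEP course. Creatinine checks are described for PrEP candidates and users (Sections VII.6, VII.8 and VII.9).
- Endpoints: the SAP lists glycosuria and quality of life. Appendix 4 lists dipstick protein only, and quality of life is not mentioned. The content of the computer-assisted questionnaire (Appendix 5) is not shown, so collection of quality of life cannot be ruled out.

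**3. The reverse direction.** The SAP text has 0 mentions of PrEP, Truvada, linkage, retention or NAT.

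**4. Can the precision of the regimen comparison be gauged?** Appendix 1 reproduces for HIV-negatives: 1,800 / 4 = 450 enrolled; 450 × 0.30 = 135 interested in PrEP; 450 − 135 = 315 not. It gives no number of PEP recipients and no split by regimen, so precision cannot be computed.

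**5. Size of the NAT conflict (illustration).** Scheduled follow-up after starting PrEP is at weeks 4, 12, 24, 36 and 48, which is 5 visits. Participants not on PrEP have visits at months 1, 6 and 12, which is 3 (Section VII.5). Assume full attendance, no as-needed visits, and that those who start PrEP stay on it for 48 weeks. Screening and week 0 are left out because the drug has not yet been started.
- All 135 start: the Section VII.3 rule gives 135 × 5 + 315 × 3 = 675 + 945 = 1,620 samples; the Appendix 12 rule gives 945. The share in dispute is 675 / 1,620 = 42%.
- Half start: 67.5 × 5 = 337.5 and 382.5 × 3 = 1,147.5, total 1,485. The share is 337.5 / 1,485 = 23%.
- None start: 0%.

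**The case against.** The strongest reply is that assigned may simply mean the regimen a clinician selected, since Section VII.6 does say that regimens are selected. A regimen is then fixed at prescription, before its outcome. That is fair for the individual participant. It still leaves no defined groups to compare, and none of the SAP's products appears.

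The second reply is that the unavailable pages, in particular the SAP text ahead of the heading seen, may define the groups. This stands. A reader might infer that the groups will be formed after the fact, but the documents show only that this could happen.

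A reader might also infer that the SAP omits the protocol's aims altogether. The documents do not support that. The only endpoint heading seen is for secondary endpoints, so primary endpoints may stand elsewhere. Several of the 8 product-neutral items, such as adverse events, seroconversion and creatinine, could also be applied to PrEP users, although the text does not say so.

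On NAT, one might cite Section VII.5 as a second statement of the every-visit rule. That section describes participants who are not on PrEP, so it agrees with Appendix 12. The conflict is between Section VII.3 and Appendix 12 only.

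Finally, one might infer that retention will be miscounted, because visits without PrEP run from enrollment while PrEP visits run from initiation, and "The PrEP initiation visit will take place 1-2 weeks after screening, when all screening results are available". The documents fix neither an enrollment date for analysis nor an analysis window. The two-week tolerance in Section VII.9 is for scheduling, and a shift of 1 to 2 weeks stays within it. That argument is not part of this point.

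**Conclusion.** The SAP text does not fit the protocol text and has to be reconciled before any analysis. The mismatch covers four endpoints tested against PEP regimen and three product-specific objectives, and it runs both ways, since Truvada PrEP is absent from the SAP text. The textual mismatch is certain for the pages seen. That the comparison lacks defined groups is conditional on the unavailable pages not supplying them, and coverage of the aims is a matter to confirm.

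It is also possible that this SAP was written for another protocol or a sub-study. The mismatch raises that question but does not settle it.

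The NAT inconsistency lies within the protocol. In the illustration it affects between 0 and 42% of scheduled follow-up samples, depending on how many of the projected 135 start PrEP. No view is taken here on which PEP regimen or testing rule is right.

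**What to change.** 1. Confirm that this SAP text belongs to the CRUSH protocol. This comes first, because otherwise the wrong document would be edited.
2. If it does, remove the PEP-regimen comparisons and the three product-specific objectives, or move them to a separately defined PEP sub-study. Keep them only if a CRUSH protocol version, or the pages not available here, defines the groups.
3. Confirm that the full SAP analyses testing and linkage, retention of HIV-positive participants, retention and PrEP use among HIV-negative participants, and NAT. If it does not, replace the PEP comparisons with descriptive estimates and 95% confidence intervals from data that Section X already brings together: study forms, demographics, visit dates, missed visits and laboratory results. The referral source asked at check-in and the coded cards for social network testing are not on that list, so the plan should say where the Aim 1 figures would come from.
4. Reconcile Section VII.3 with Appendix 12 and state the NAT denominator, by participants and by visits, to match.

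The cost is rewriting the SAP and aligning two protocol passages. No participants or visits are added.

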Symptoms and laboratory parameters associated with potential toxicities of FTC/TDF will be monitored as described above. As is true for all patients of EBAC/DYC, study participants will have received instructions for contacting the clinic to report any adverse signs or symptoms that they experience. Grade 3 or 4 adverse events, as defined by the DAIDS Table for Grading the Severity of Adult and Pediatric AEs, Version 1.0, December, 2004 (Clarification August 2009) will be recorded on the Adverse Event form. All Adverse Events will be evaluated by an EBAC/DYC clinician. Symptomatic Grade 3 events and Grade 4 adverse events will be reported to CHRP and Gilead Sciences by the investigators regardless of relation to the study drug.

IX. 1.1 Creatinine elevation

For an estimated glomerular filtration rate (eGFR) less than 60 ml/min/1.73m², serum creatinine will be repeated as soon as possible within 7 days. If the eGFR remains less than 60, FTC/TDF will be held until the eGFR is again greater than 60, at which point the participant may be re-challenged with FTC/TDF after consultation with the Principal Investigator ([name]). If the eGFR again falls below 60 after the drug is restarted, FTC/TDF will be permanently discontinued, and the participant will be monitored until the eGFR returns to baseline or stabilizes.

IX. 2 Urine protein detection

Any participant with protein of 1+ or greater on urine dipstick analysis will have the urine dipstick repeated within a week. If the creatinine is normal and the repeat dipstick is < 2+ the participant may remain on PrEP. Participants who have dipstick of $\geq 2+$ will have PrEP discontinued and will be referred to a nephrologist. If the nephrologist does not recommend against restarting PrEP, the participant can restart. Participants with evidence of renal toxicity attributable to FTC/TDF will have the study drug stopped

IX. 3 HIV acquisition /suspected acute HIV infection

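### The SAP plans only a mean and SD for creatinine change and no count of renal declines, so a few large declines could go unseen

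*SAP*

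**What the plan says.** The SAP, under Secondary Endpoints(s), opens with a renal objective, "To assess the renal safety of Stribild® or Genvoya" (or the unbranded equivalent) given as PEP. It lists "Change from baseline in serum creatinine and eGFR" as an endpoint, and also glycosuria and proteinuria above 1+ as markers of tubular damage.

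The analysis section has one creatinine-specific sentence: "Changes in serum creatinine will be summarized with descriptive statistics (mean, standard deviation", followed by a comparison with earlier trial data. A general sentence comes before it: "Descriptive statistics (frequencies, means, medians) will be used to characterize endpoint variables". The section also tests associations with "key endpoints such as adherence, early cessation of regimen, and frequency of adverse events". In the SAP text supplied, eGFR has no analysis of its own, no renal threshold is defined, no time point or analysis set is named for the creatinine summary, and no rule covers unscheduled values or values taken after drug is stopped.

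The protocol treats renal decline as an individual event. Section IX. 1.1 calls for a repeat creatinine within 7 days when eGFR is below 60, and then: "If the eGFR remains less than 60, FTC/TDF will be held until the eGFR is again greater than 60". A second fall after restarting leads to permanent discontinuation. That section is about FTC/TDF PrEP.

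**The concern.** A mean answers whether the group as a whole shifted. A safety reader also needs to know how many people had a material decline, and how large the worst was. If harm falls on a few participants, the unaffected majority dilutes it. The report could then describe creatinine as essentially unchanged while several participants had crossed a threshold that the protocol itself acts on. Setting the mean beside a historical mean does not help, because both are diluted in the same way.

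**Working it through.** **Plan's own figures.** The documents give no renal sample size, SD, event rate or margin, so there is no renal figure to reproduce. The nearest denominator is the Appendix 1 projection of HIV-negatives interested in PrEP, and it reproduces:
- Tests: 675 per year × 2.75 years = 1,856.25 (stated 1,857).
- Positives among them: 0.025 × 1,718.75 + 0.10 × 137.5 = 56.7. Negatives: 1,799.5 (stated 1,800).
- A quarter enrol: 449.9 (stated 450). Of these, 30% × 450 = 135 (stated 135).

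The number of PEP recipients is not given, so 135 serves only as an illustrative size.

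**Assumptions (not from the documents).** N = 135. Four participants have a creatinine rise r of 0.3, 0.5 or 0.6 mg/dL. The others have mean change 0 and SD s of 0.10 or 0.12 mg/dL. All peak values are captured.

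**Formulas.** With p = 4/135 = 0.0296 and p(1−p) = 0.02875:
- mean shift = p × r
- total SD = √(s² + p(1−p) × r²)
- 95% half-width = 1.96 × total SD / √135

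| Rise r | Mean shift | Half-width, s = 0.10 | Half-width, s = 0.12 |
|---|---|---|---|
| 0.3 | 0.009 | 0.019 | 0.022 |
| 0.5 | 0.015 | 0.022 | 0.025 |
| 0.6 | 0.018 | 0.024 | 0.027 |

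Worked row, r = 0.5 and s = 0.10: shift = 0.0296 × 0.5 = 0.0148; SD = √(0.0100 + 0.00719) = 0.131; half-width = 1.96 × 0.131 / 11.62 = 0.022.

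In every cell the shift lies inside its own uncertainty. The same data as a proportion are 4/135 = 3.0%, Clopper-Pearson 95% CI 0.8% to 7.4%.

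**Where masking ends.** With 7 cases (5.2%), r = 0.5 and s = 0.10, the shift is 0.026 against a half-width of 0.025, so the mean just begins to show it. Sample size matters too. At 3.0%, r = 0.5 and s = 0.10, shift and half-width are equal at N = (1.96 × 0.1311 / 0.0148)² ≈ 300. A smaller group makes masking easier and a larger one harder.

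**Do the other planned items count eGFR declines?**
- Tubulopathy markers are urine findings, a different measurement from eGFR.
- Early cessation is not split by cause. A hold followed by the re-challenge that IX. 1.1 permits need not count as cessation.
- Adverse-event frequency is not split by cause either. Section IX requires Grade 3 or 4 events to be recorded but does not say that an eGFR hold is itself recorded as an event.
- The general promise of frequencies defines no renal category to be counted.

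**The case against.** The strongest reply is that renal safety does not rest on the creatinine mean alone. eGFR change and tubulopathy markers are listed, frequencies are promised for endpoint variables, and cessation and adverse events are analysed. The inventory in Appendix 7 also records whether drug was interrupted or withdrawn. This is correct as far as it goes, and it is why the point is limited to creatinine and eGFR. None of these routes yields a count of eGFR declines.

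A reader might also infer that the hold rule takes the worst cases off drug and so biases the creatinine mean toward no change. The documents do not support that. The qualifying eGFR and its repeat both come before any hold, and monitoring continues after a permanent stop. The SAP does not specify a mean by visit. Above all, the hold rule is written for FTC/TDF PrEP, with visits to week 48 and beyond, while the SAP concerns PEP, which Section VII.6 of the protocol describes as a 28-day course. No document applies the hold rule to the SAP's regimen.

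The illustration is open to challenge as well, since the case number, rises and SD are all assumed. With no background variation at all, four rises of 0.6 give SD 0.102 and SE 0.102/√135 = 0.0088, so the mean of 0.018 is about 2 SE from zero. That objection stands to this extent: masking depends on the inputs. Real creatinine change does vary between people, however, and even a detectable shift of 0.018 would not tell the reader that four people each rose by 0.6. The planned SD would be somewhat inflated by such cases, but it does not identify or count them.

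**Conclusion.** The point holds in limited form. The only analysis specified for creatinine change is a mean and SD against historical data. No count of renal declines is planned, although renal safety is an objective. Under the stated assumptions, about 3% of 135 participants with rises of 0.3 to 0.6 mg/dL would shift the mean by no more than 0.018 mg/dL, within its 95% half-width. At about 5% with a rise of 0.5 the shift reaches the edge of detectability. Declines could therefore be masked; the documents do not show that they would be. Nor do they support saying that renal safety as a whole is reduced to one mean, or that the hold rule biases it.

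The mismatch of regimens between protocol and SAP limits how far the figure of 135 and the eGFR threshold carry over, and it has to be settled first. The need for a count remains whichever regimen the analysis covers.

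**What to change.** 1. Reconcile protocol and SAP on which regimen, and which participants, the renal analysis covers.
2. Add to the SAP's analysis section the number and percent, with exact 95% CI, of participants with confirmed eGFR below 60, and of those whose drug was interrupted or stopped for renal reasons. The value 60 is used as a reporting cut-point because the protocol already names it; this implies nothing about clinical management of either regimen.
3. Report each participant's largest post-baseline change in creatinine and in eGFR, including unscheduled repeats.
4. Flag values taken after a hold or stop as off-drug, but keep them in the report. Leaving them out would remove the affected participants from later summaries and bring back the problem.
5. Keep the planned mean and SD, and name the time points and analysis set.

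The cost is a short SAP amendment and one extra safety table. Creatinine results are laboratory data, which Section X already links from the electronic record. Interruptions and stops are not laboratory data and would have to come from the study forms, where the Appendix 7 inventory has codes for them; the renal reason would need to be captured. No extra visits or samples are needed.
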